5.2.2 Trial Stopping Rules

In the event of a death definitely related to study drug within 24 hours of vaccination or ≥ 3 definitely related SAEs (per 20 patients) at any time after receiving study drug during the treatment period, dosing will halt immediately and the DMC will be consulted. All data will be reviewed prior to any further dosing, and dosing will not continue until the DMC agrees that it is safe to continue. At the discretion of the DMC, the FDA or other Health Regulatory Agencies may be consulted. The decision to permanently halt the trial may only be made by BNI Executive Committee.

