1.2.7 Vaccinia Virus

Vaccinia virus has been used for over 200 years as a vaccine for smallpox and has a well-established safety and adverse event (AE) profile (Casey 2005, Poland 2005). The virus actively replicates in human cells, and generates a strong inflammatory response, resulting in the presentation of high levels of antigen to the immune system over a period of one to two weeks, supporting a potent immune stimulation. Subsequently, the immune response specific to vaccinia then eliminates the virus. Host immune responses to vaccinia restrict its replication and thus limit its ability to be re-used for subsequent

vaccinations. Consequently, vaccinia-based vaccines, although potent immunological priming agents, can be used to immunize an individual only once or twice.

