1.5 Safety of Poxviral Vectors

1.5.1 Vaccinia Virus

Vaccinia virus causes a transient infection, with elimination of viral components over several weeks. Host cells infected with vaccinia virus are short lived (days) and die by a mixed form of apoptosis/necrosis. Vaccinia replicates in the cytoplasm of infected cells, and viral DNA does not integrate into the host cell DNA. Vaccinia virus is known to be shed from the wound site in traditional dermal scarification based vaccination.

The use of vaccinia virus for worldwide eradication of smallpox provides a safety database with number of observations in the millions. Geographical differences in strains of vaccinia virus used as well as differences in reporting practices, diagnostic and follow-up criteria between countries are a cause of some discrepancies in the incidences of adverse events reported, but the overall picture of vaccinia virus safety is very well known. An additional set of data is provided by recent vaccination campaign of military and civilian vaccinations in the US.

A number of events post vaccination are expected and considered to be normal: fever, myalgia, headache, fatigue, chills, nausea, soreness and erythema at the vaccination site, local lymphadenopathy. Satellite lesions around the vaccination site have been reported as well as local edema. These symptoms are self-limiting, last for around three weeks after vaccination and rarely are a cause for serious concern (Frey 2002, Fulginiti 2003). Mild adverse reactions that can occur post vaccination are bacterial superinfection of vaccination site, erythema multiforme (EM) and generalized vaccinia. Superinfection is a rare event with incidence from 0.14 to 55 cases per million according to different reports (Vellozzi 2004). EM most often presents as papules, plaques or urticaria which may be symmetrical, may involve palms and soles. EM resolves spontaneously and requires no special care. A development of Stevens-Johnson syndrome with mucosal involvement is extremely rare, with only one case noted in the 2003-2004 vaccination campaign in the US (<1 per 1,000,000) (Fulginiti 2003, Neff 2008).

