Generalized vaccinia results from viremic spread of vaccinia virus from the vaccination site. It presents as a generalized rash, which behaves like the vaccination site lesion, progressing through papular, vesicular, pustular and scab-forming stages. The incidence is difficult to assess, since historically there was no strict definition to distinguish generalized vaccinia from other conditions where rash is a dominant symptom (severe chickenpox, smallpox, eczema vaccinatum, EM). Retrospective analysis of 2002 – 2004 vaccinations suggests an incidence of ~50 cases per 1,000,000 (Bryant-Genevier 2006). The rash appears within a week after vaccination and resolves within a week. Most instances do not require specific therapy (Fulginiti 2003).

Some of the post-vaccinia adverse events, although very rare, are serious and potentially life-threatening. They are described as follows.

Progressive vaccinia (PV) is the most serious complication known. It was almost always fatal prior to the introduction of vaccinia immune globulin (VIG). PV occurs predominantly in persons with T-cell deficiencies or receiving treatments that result in T-cell deficiencies. The primary vaccination site fails to heal leading to a severe local reaction with necrosis, and viremic spread of vaccinia leads to generalized appearance of new lesions without reactive immunoinflammatory response (Bray 2003, Fulginiti 2003). PV is extremely rare; historical incidence is in the order of 1 case per 1,000,000. There were no reports of PV in the military and civilian vaccines in 2002 – 2004 vaccination campaigns (Neff 2008).

Eczema vaccinatum (EV) manifests as rash (papular, vesicular, pustular, erosive) that can be localized or generalized and predominantly occurs in the areas that have been affected by lesions of atopic dermatitis or other eczematous skin condition. Historically it occurred at a rate of ~1 case per 25,000 vaccinations.

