In the recent series of military and civilian vaccinations, vaccinia immunization has been reported to induce myopericarditis. Symptoms of chest pain were typically mild and transient, but occurred in 1/1,000 subjects. The incidence of this complication is lower in re-vaccinees. To prevent potential exacerbation of existing chronic problems, this protocol excludes subjects with known history of heart disease from participating in the trial. In addition, there are rare risks of severe and possibly life-threatening adverse reactions. These include eczema vaccinatum (~1/25,000, usually with history of underlying skin disorder) or progressive vaccinia infections (~1/300,000, usually with underlying immunodeficiency), or post vaccinia encephalitis (~1/500,000, usually infants or small children). These were observed after the administration of conventional smallpox vaccines, and have not been seen in prior studies of PROSTVAC-V/F or related PSA (or other tumor antigen-containing vaccinia virus vaccines) administered to vaccinia pre-immune cancer subjects. Under the proposed protocol, age restriction, exclusion of all pre-existing conditions with features of immune suppression and skin disorders minimize the risk of such rare complications.

During study treatments, subjects will be under the continuous care of the investigator and his/her staff and will be assessed for adverse events which will be recorded in the subject's CRF. SAEs must be reported to BNI or its designee within 24 hours of discovery. To minimize risk, potential subjects who have a known allergy to eggs, egg products, aminoglycoside antibiotics or GM-CSF, or other pre-existing medical conditions known to be risk factors for SAEs will be excluded from participation.

In view of the anticipated mild side effects, the potential risks for the subject seem to be limited and to justify the potential benefit of participating in this trial.

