2.3 GM-CSF

GM-CSF (Leukine[®]: 250 μg , lyophilized) will be purchased from licensed, US pharmacy wholesalers and labeled appropriately for the study. Lyophilized GM-CSF will be reconstituted using 1.0 ml of room temperature bacteriostatic water for injection (USP-grade or equivalent). Product reconstituted with bacteriostatic water for injection is stable for 20 days if stored between 2 and 8°C in the original vial. See product label for information related to product description and formulation. Doses of GM-CSF of 100 μg each will be drawn into labeled syringes by an independent, unblinded research pharmacist or designee for use by the clinic staff or by individual subjects for home injection (subjects enrolled in France must return to the clinic to receive GM-CSF injections).

Dose: 0.40 ml (100 μg) GM-CSF

Route of administration: Subcutaneous injection

Storage: 2 - 8°C (lyophilized and reconstituted); Up to 4 days at 2 - 8°C when in syringes

Regimen of administration: GM-CSF will be injected sc by the study staff on the day of vaccine or placebo administration and for the subsequent 3 days, within approximately 5 mm of the injection site by the study staff, the subject, or subject's caregiver (subjects enrolled in France must return to the clinic to receive GM-CSF injections).

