5.0 SAFETY MONITORING

5.1 Data Monitoring Committee (DMC)

An independent Data Monitoring Committee will be established to ensure subject safety, to consider subject risks against the potential for meeting trial objectives, and to provide recommendations to BNI with respect to the conduct and analysis of the trial. The DMC will operate independently of BNI with the exception of the administration of compensation to the DMC members for DMC-related activities and non-voting activities such as clinical trial conduct updates. The voting members of the DMC will be a multi-disciplinary group that may include representative physicians who treat the type of subjects entered onto this trial; one or more individuals with statistical expertise; and if appropriate, one or more biological scientists. The DMC will meet either by phone or in person and will be provided with all available pertinent subject data in a manner specified in the approved Charter. An Executive Summary of Committee recommendations generated at each meeting will be forwarded to all IRBs/ECs as requested or required. Minutes of the closed sessions will be held in confidence by the DMC or its designee until the official close of the trial. The exact constitution and conduct of the DMC will be ultimately governed by the approved Charter. A vital status sweep will be performed in conjunction with each DMC meeting to ensure the most current data is being reviewed.

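### Protocol 5.2.2 makes one definitely related death an automatic dosing halt only if it falls within 24 hours of vaccination; a later one counts as a single SAE toward three per 20 patients

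*Protocol*

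**What the plan says.** Protocol 5.2.2 has two triggers joined by 'or'. The first is "In the event of a death definitely related to study drug within 24 hours of vaccination". The second is three or more "definitely related SAEs (per 20 patients) at any time after receiving study drug during the treatment period". Either one stops dosing at once, and dosing resumes only when the DMC agrees that it is safe.

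Under Protocol 8.8, a death from a cause other than disease progression is reported as an SAE. Protocol 8.12 collects new SAEs until 28 days after the last dose of study medication.

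On the vaccinia prime, Protocol 1.2.7 describes replication "resulting in the presentation of high levels of antigen to the immune system over a period of one to two weeks", and 1.5.1 says: "Vaccinia virus causes a transient infection, with elimination of viral components over several weeks". Of progressive vaccinia, which 1.5.1 calls the most serious known complication, the protocol writes: "The primary vaccination site fails to heal leading to a severe local reaction with necrosis", with viremic spread to new lesions. Section 1.6 accepts that "there are rare risks of severe and possibly life-threatening adverse reactions".

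On oversight, Protocol 5.1 states: "The exact constitution and conduct of the DMC will be ultimately governed by the approved Charter".

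**The concern.** The time limit in the first trigger belongs to the death, and the 'at any time' wording belongs to the SAE count. Reading 'at any time' into the death trigger would leave the 24-hour limit with no meaning. So a death that the investigator has already classed as definitely related halts dosing automatically on day 1 but not on day 10.

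A non-healing wound with later spread is hard to fit into 24 hours, so the limit appears to miss the kind of death that the protocol's own account of vaccinia would suggest. Followed literally, the rule lets other men go on being dosed by default until someone decides otherwise. What is at stake is patient safety during the review of such a case. The efficacy analysis and its error rates are not affected.

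**Working it through.** The protocol gives no operating characteristic for this rule, so there is no figure to reproduce. The check is a reading of the text, followed by a rough count of expected events.

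**1. Which trigger catches a definitely related death on day 10 after the prime?**
- Death trigger: no, because more than 24 hours have passed. The next vaccination is due in Week 3.
- SAE trigger: it supplies one of the three events needed (8.8 makes it an SAE). Two more are needed within the '20 patients', unless the man who died had earlier definitely related SAEs.
- The SAE trigger is confined to the treatment period, which 5.2.2 does not define. Section 8.7 moves a man with intolerable toxicity straight into long-term follow-up. Whether his later death still falls in the treatment period is not stated.

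**2. Does anything else require a halt?**

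| Provision | Section | Effect |
|---|---|---|
| DMC review | 5.1 | Recommends; governed by the Charter |
| Dose-limiting toxicity | 5.2.1 | Stops study drug for that man only |
| Sponsor discontinuation | 5.4, 12.1 | Permits a stop |
| Serious vaccinia reaction plan | 6.8 | Notification and treatment |
| SAE reporting within 24 hours | 8.13, 8.14 | Informs |
| SUSAR reporting, investigator letters, internal safety committee | 8.11 | Informs and escalates |

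None of these mandates a trial-wide halt in dosing.

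**3. How does 24 hours compare with the periods the protocol describes?**
- High-level antigen presentation after vaccinia: one to two weeks (1.2.7).
- Ordinary post-vaccination symptoms: around three weeks (1.5.1).
- Viral elimination: several weeks (1.5.1).
- Contact precautions after the first vaccination: three to four weeks or until the site heals (exclusion 20).
- SAE collection: to 28 days after the last dose (8.12).

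These are durations of infection, reaction and surveillance. The protocol gives no time to death for any complication, so a fatal case after 24 hours is inferred from the described course. Replicating vaccinia is given once, in Week 1. The other six vaccinations are fowlpox, which does not replicate in human cells (1.2.8).

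**4. How many events might there be?** Two vaccine arms of 400 give 800 men. Protocol 1.6 gives approximate smallpox-vaccine rates:
- Eczema vaccinatum: 800 × 1/25,000 = 0.032
- Progressive vaccinia: 800 × 1/300,000 = 0.0027
- Encephalitis: 800 × 1/500,000 = 0.0016
- Total: 0.036 cases, fatal or not

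Section 1.5.1 quotes other rates: about 1 per million for progressive vaccinia and 5 per million for encephalitis in the 2002–2004 US programme. These give 0.0008 and 0.004, and the total becomes 0.032 + 0.0008 + 0.004 = 0.037, practically unchanged.

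The total ignores the exclusions. Eczema vaccinatum supplies 0.032 of the 0.036, and exclusion 18 removes men with atopic dermatitis or active skin disease. Without it, 0.0027 + 0.0016 = 0.0043 cases remain. At the 25% historical case fatality in 1.5.1, encephalitis contributes 0.0016 × 0.25 = 0.0004 deaths.

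The total also leaves out myopericarditis. At the 1/1,000 in 1.6 that is 800/1,000 = 0.8 cases, described there as typically mild and transient and less frequent in re-vaccinees. Prior smallpox vaccination is an entry requirement here.

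**The case against.** The strongest reply is that 5.2.2 is a floor. It pairs an acute-death trigger with an SAE-rate trigger and leaves the rest to the DMC and sponsor. A definitely related death would reach the sponsor within 24 hours and, if a SUSAR, would go to regulators and all investigators. A reader might infer that the trial would simply carry on dosing after a vaccine death. The documents do not support that: several bodies would know quickly and could stop. What remains is that none of them is obliged to, and the protocol already treats one related death as reason enough for a mandatory halt if it is early.

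A second reply is that the hazard is narrow and remote: one dose in seven, given subcutaneously to pre-immune men, with skin disease and immunodeficiency excluded. Section 1.6 reports none of the three severe complications in earlier PROSTVAC-V/F studies. This stands, and it keeps the severity low. It also rules out reading a weeks-long fatal hazard into every vaccination. Rarity does not, however, explain why the limit should be 24 hours.

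A reader might also conclude that the SAE trigger would almost never catch a late death. That cannot be shown. The documents give no rate of definitely related SAEs, and 'per 20 patients' could mean fixed blocks, consecutive men, a running rate or any 20 men in the trial. The answer depends heavily on which is meant.

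Finally, the Charter may already contain a wider halt. That is possible and could not be checked.

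**Conclusion.** The gap is real on the text. A single definitely related death more than 24 hours after vaccination does not by itself halt dosing under 5.2.2, and no other section of the protocol or SAP requires it to. The window is shorter than the described course of the vaccinia prime and shorter than the 28-day SAE window.

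The size is very small: about 0.04 cases of the three severe complications in 800 men at the protocol's rates, fewer after the exclusions, and only some fatal. The conclusion rests on three things: the literal reading of 5.2.2, the inference that a fatal vaccinia complication would take longer than 24 hours, and the absence of a wider rule in the unseen Charter. It is a low-severity point, worth making because the harm is irreversible and the correction is cheap.

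**What to change.** Replace the death trigger in 5.2.2 with: *any death definitely related to study medication (study vaccine, GM-CSF or placebo) from first dose through 28 days after the last dose*. Keep the same temporary halt and DMC review, and check that the Charter matches.

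'Study medication' is the term defined in section 8.0. It suits the rule because the present limit is timed from vaccination, whereas under Protocol 2.3 "GM-CSF will be injected sc by the study staff on the day of vaccine or placebo administration and for the subsequent 3 days". This is a matter of consistent wording; no document ties the later injections to a fatal risk.

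The cost is one sentence in the protocol, any matching Charter edit, and a small chance of one extra temporary pause. Pauses should stay rare because 8.5 classes an event that could also be due to the underlying disease as only possibly related. The same definition limits what the wider trigger will catch.

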5.3 Emergency Unblinding Of Treatment Assignment (If Applicable)

All investigational vaccine products for this study have been packaged and labeled in a blinded fashion. GM-CSF will be labeled for investigational use as required by the local and regional Health Authorities, Lyophilized GM-CSF is not packaged and labeled in a blinded fashion. Reconstituted GM-CSF or GM-CSF placebo in single-use syringes is blinded. Unblinding by study site personnel for adverse events should only be performed in emergencies where knowledge of the subject's treatment assignment is essential for further management of the subject's medical care. Unblinding a subject's treatment assignment under any other circumstances will be considered a protocol violation. The Principal Investigator is strongly encouraged to contact the BNI Medical Monitor before unblinding any subject's treatment assignment, but must at least do so within 1 working day after the unblinding. Although the Medical Monitor should be contacted the subject's treatment code should not be communicated to the Medical Monitor. Emergency unblinding for adverse events will be performed through an interactive voice-response system (IVRS). All calls resulting in an unblinding event are recorded and reported by the IVRS. Emergency unblinding must also be documented at the study site. The Medical Monitor will receive notification of unblinding from IVRS but will not be notified of the subject's treatment assignment.

5.4 Removal of Subjects from Therapy or Assessment

Subjects may withdraw consent for participation in the study at any time without prejudice. Additionally, the investigator may withdraw a subject if, in his/her clinical judgment, it is in the best interest of the subject or if the subject cannot or will not comply with the protocol. Wherever possible, the End-of-Study tests and evaluations listed in [Section 7.4](#) should be carried out at the time the subject withdraws or whenever the Investigator feels that the subject will be unable to make any further visits.

If a subject fails to return for the necessary visits or discontinues prematurely from the study, a genuine effort must be made to determine the reason why. If the subject or his designated contact is unreachable by telephone, the minimum of a registered letter should be sent requesting that contact be made with the Investigator (or designee) to report survival information. Every attempt possible to obtain follow-up blood samples for safety and immune monitoring should be made. Request for an autopsy, autopsy report and death certificate when/if the subject expires while on trial should be pursued.

BNI may discontinue individual subjects, study arms, individual study centers, or the entire study at any time provided sufficient time is given to ensure subject safety.

5.4.1 Clinical or Kinetic Progression: Removal of Subjects from Therapy

Subjects who experience a significant clinical progression during the treatment phase (i.e., before last vaccination is received) will be counseled to seek alternative therapy. Significant clinical progression is defined by the need to institute scheduled narcotic pain relief measures for cancer-related pain, or acceleration of tumor growth kinetics by PSA (PSA doubling time <1 month). Such subjects are allowed to continue vaccine therapy at the discretion of the PI if the decision is made not to seek alternative anti-cancer treatment(s). If subjects choose to initiate alternative anti-cancer treatment, vaccination will be discontinued. All subjects will continue on study and will be followed for survival and safety per protocol.

5.4.2 Biochemical or Radiological Progression: Continuation of Therapy

Vaccination may take several months to induce an immune response. PSA declines and radiological responses are infrequent, and the expectation is for a slowing of ongoing disease progression. Due to the delayed effect of vaccine induced immunotherapy, PSA progression and radiological progression may be expected during the treatment phase of the trial, and are not a cause for stopping vaccination. Continued vaccination to maximize immune response is believed to be beneficial based on earlier clinical trials.

5.5 Replacement Policy

5.5.1 Subjects

No subjects will be replaced in this study. All subjects who receive at least one dose of PROSTVAC-V/F or placebo will be considered evaluable and will be included in all appropriate analyses as described in [Section 9.0](#).

5.5.2 Research Centers

Centers will be opened only after all requirements for documentation have been met as defined by Appendix M (M-I-C-1) of the NIH Guidelines for Research Involving Recombinant DNA Molecules (April 2002) or the appropriate regional or national guidelines outside the United States. If an approved institution declines further participation or is dropped for any reason, or if enrollment lags, new centers may be added under the same restrictions.

